4.0 STAGING CRITERIA (AJCC 7th Edition, 2010)

Colon

Stage IIIC

T4a T3-T4a T4b	N2a N2b N1-N2	M0 M0
Stage IIIC T3c Any T	Ovarian N0 N1	M0 M0
STAGE IIIC T1-4b T1-4b T1-4b Any T	Melanoma N1b N2b N2c N3	M0 M0 M0 M0
Stage IV Any T	Melanoma Any N	M1

Distant Metastasis (M)

M1	Distant metastasis
	Distant inclusions

M1a Metastases to skin, subcutaneous or distant lymph nodes

M1b Metastases to lung

M1c Metastases to all other visceral sites or distant metastases to any site combined with an elevated serum LDH

NOTE: for all other disease sites Stage IV is defined as any distant metastasis for this study.

5.0 ELIGIBILITY CRITERIA

Each of the criteria in the following section must be met in order for a patient to be considered eligible for registration. Use the spaces provided to confirm a patient's eligibility. For each criterion requiring test results and dates, please record this information on the Onstudy Form and submit via Medidata Rave® (see Section 14.0). Any potential eligibility issues should be addressed to the Data Operations Center in Seattle at [name] prior to registration.

In calculating days of tests and measurements, the day a test or measurement is done is considered Day 0. Therefore, if a test is done on a Monday, the Monday 2 weeks later would be considered Day 14. This allows for efficient patient scheduling without exceeding the guidelines. If Day 14, 28 or 42 falls on a weekend or holiday, the limit may be extended to the next working day.

SWOG Patient No Patient's Initials (L, F, M)			
		a.	Patients must have $BRAF^{V600}$ mutant metastatic cancer irrespective of the histology or prior therapy. $BRAF^{V600}$ mutant status must be documented by a CLIA-certified laboratory. Use of an FDA-approved test is preferred although other BRAF tests at a CLIA-certified laboratory may also be accepted.
		b.	Patients must have locally advanced unresectable Stage IIIC or metastatic Stage IV cancer with either progression to prior therapy or a newly diagnosed cancer that does not have an available treatment with curative intent. See Section 4.0 for staging criteria.
		C.	Patients must have a complete physical examination and medical history within 28 days prior to registration.
		d.	Patients must have measurable or non-measurable disease as defined in Section 10.1 . All measurable lesions must be assessed (by physical examination, CT, or MRI scan) within 28 days prior to registration. Tests to assess non-measurable disease must be performed within 42 days prior to registration. All disease must be assessed and documented on the Baseline Tumor Assessment Form (RECIST 1.1).
		e.	All patients must undergo a CT or MRI of the brain within 42 days prior to registration. Patients with asymptomatic brain metastases or previously treated brain metastases that are stable (i.e. not requiring corticosteroids) at the time of registration will be eligible.
		f.	Patients may have received prior systemic therapy (chemotherapy, immunotherapy, biologic therapy, or combination regimens). All adverse events associated with prior treatment must have resolved to \leq Grade 1 prior to registration.

swog	Patient	No	
Patient'	's Initia	ls (L, F,	M)
		g.	Patients progressing on a prior BRAF inhibitor-based therapy will be eligible, as are patients naïve to BRAF inhibitor therapy. Resistance to BRAF inhibitor-based therapy will be defined as progressive disease by RECIST 1.1 criteria while receiving therapy with a BRAF inhibitor (vemurafenib or dabrafenib, alone or in combination with a MEK inhibitor). This may be innate resistance (patients who never achieved a tumor response while on BRAF inhibitor therapy) or acquired resistance (progression after having a tumor response to BRAF inhibitor therapy). There will not be a period of break between progression on the prior BRAF inhibitor-based therapy and the start of dabrafenib, trametinib and GSK2141795.
		h.	Patients may have received prior surgery (for both the primary and Stage IV disease). All adverse events associated with prior surgery must have resolved to ≤ Grade 1 prior to registration.
		i.	Patients may have received prior radiation therapy. All adverse events associated with prior radiation therapy must have resolved to \leq Grade 1 prior to registration.
		- j.	Patients must be willing to submit blood for pharmacokinetics (see Section 15.3). Sites must order S1221 PK kit immediately after registration (see Section 18.6). The SWOG patient ID number must be provided on the S1221 PK Kit Request Form.
		k.	Patients must have available and be willing to submit baseline tissue taken at the time of disease progression to prior BRAF inhibitor-based therapy (either fresh frozen [preferred], or paraffin-embedded tumor blocks) OR must have a site of disease that can be biopsied within this study for translational medicine studies outlined in Section 15.4 and Section 18.2 . Tissue may be from an archival biopsy or a new biopsy after the patient has been registered to the protocol. Since patients are referred to this protocol after progression on prior BRAF inhibitor-based therapy, the biopsy taken at the time of progression will be used as the baseline biopsy for this study. Patients must be willing to submit plasma and whole blood for translational medicine studies as outlined in Section 15.4 and Section 18.2 .
		. I.	Patients must have Zubrod Performance Status ≤ 1 (see Section 10.4).
		m.	Patients must have adequate bone marrow function as evidenced by all of the following: ANC \geq 1,200/ul; platelets \geq 100,000/ul; and hemoglobin \geq 9 g/dL. These results must be obtained within 28 days prior to registration.
		n.	Patients must have adequate liver function as evidenced by the following: total bilirubin ≤ 1.5 x institutional upper limit of normal (IULN) (or ≤ 2.5 x ULN for patients with Gilbert's syndrome), and AST and ALT ≤ 2.5 x IULN (or < 5 x IULN for patients with known liver metastases). Patients must have a serum albumin ≥ 2.5 g/dL. These results must be obtained within 28 days prior to registration.

SWOG Patient	t No	
Patient's Initia	ıls (L, F,	M)
	· O.	Patient must have adequate renal function as evidenced by ONE of the following: serum creatinine ≤ 1.5 mg/dL OR measured or calculated creatinine clearance ≥ 50 mL/min. This result must have been obtained within 28 days prior to registration.
		Estimated creatinine clearance = (140 - age) x wt (kg) x 0.85 (if female) 72 x creatinine (mg/dl)
	· р.	Patient must have a left ventricular ejection fraction ≥ institutional lower limit of normal (LLN) by ECHO or MUGA within 28 days prior to registration.
	. q.	Patients must not have a corrected QT (QTc) interval ≥ 480 msecs within 28 days prior to registration
	- r.	Patients must not have a history of acute coronary syndromes (including unstable angina), myocardial infarction within 6 months, coronary angioplasty, or stenting within the past 24 weeks; Class II, III, or IV heart failure as defined by the New York Heart Association (NYHA) functional classification system (see Appendix 18.6); or history of known cardiac arrhythmias (such as atrial fibrillation) unless it has been stably controlled for > 30 days prior to registration. Abnormal cardiac valve morphology (≥ Grade 2) documented by echocardiogram (subjects with Grade 1 abnormalities [i.e., mild regurgitation/stenosis]) can be entered on study. Subjects with moderate valvular thickening are not eligible.
	· S.	Patients with melanoma must have a serum lactate dehydrogenase (LDH) test performed within 28 days prior to registration.
	. t.	Patients with HIV are eligible if they are not on antiviral agents and have adequate CD4 counts (≥ 500 mm³).
	. u.	Patients receiving anticoagulation treatment are allowed to participate with INR established within the therapeutic range. (See Section 7.2b).
	· V.	At the time of registration, patients must not be receiving any medications or substances that are strong inhibitors or inducers of CYP3A or CYP2C8. Patients must not be planning to use herbal remedies (e.g., St. John's wort), or strong inhibitors or inducers of P-glycoprotein (Pgp) or breast cancer resistance protein 1 (Bcrp1). See Appendix 18.4 for list of medications.
	. W.	Women of childbearing potential must have a negative pregnancy test within 14 days of registration.

SWOG Patient	No	
Patient's Initial	ls (L, F,	M)
	x.	Patients must not be pregnant or nursing due to unknown teratogenic side effects. Women/men of reproductive potential must have agreed to use an effective contraceptive method. A woman is considered to be of "reproductive potential" if she has had menses at any time in the preceding 12 consecutive months. In addition to routine contraceptive methods, "effective contraception" also includes heterosexual celibacy and surgery intended to prevent pregnancy (or with a side-effect of pregnancy prevention) defined as a hysterectomy, bilateral oophorectomy or bilateral tubal ligation. Hormonal contraception is not allowed due to drug interactions which can render hormonal contraceptives ineffective. However, if at any point a previously celibate patient chooses to become heterosexually active during the time period for use of contraceptive measures outlined in the protocol, he/she is responsible for beginning contraceptive measures.
	y.	Patient must not have uncontrolled intercurrent illness including, but not limited to, ongoing or active infection, previously diagnosed Type 1 diabetes mellitus/Type 2 diabetes, psychiatric illness/social situations, symptomatic congestive heart failure, unstable angina pectoris, cardiac arrhythmia, that would limit compliance with study requirements. Patients must not have any evidence of mucosal or internal bleeding. Patients must not have a history of pneumonitis or interstitial lung disease. Patients must not have received any major surgery within four weeks prior to registration.
	Z.	Patients must not have an active Hepatitis B Virus (HBV) or Hepatitis C Virus (HCV) infection.
	aa.	Patients must not have a history of allergic reactions attributed to compounds of similar chemical or biologic composition to dabrafenib or other agents used in this study including dimethyl sulfoxide (DMSO).
	bb.	Patients must be able to retain oral medication and must not have any clinically significant gastrointestinal abnormalities that may alter absorption such as malabsorption syndrome or major resection of the stomach or bowels. Patients who have feeding tubes can enroll in the study provided that the capsules do not need to be modified.
	CC.	Patients or their legally authorized representative must be informed of the investigational nature of this study and must sign and give written informed consent in accordance with institutional and federal guidelines.
	dd.	As a part of the OPEN registration process (see Section 13.3 for OPEN access instructions) the treating institution's identity is provided in order to ensure that the current (within 365 days) date of institutional review board approval for this study has been entered in the system.
	ee.	Patients must be ≥ 18 years of age.
	ff.	Patients must have a serum albumin ≥ 2.5 g/dL within 28 days prior to registration.

SWOG Patient	No		
Patient's Initials (L, F, M)			
	gg.	Patients with known history or current evidence of retinal vein occlusion (RVO) are not eligible:	
		 History of RVO, or predisposing factors to RVO (e.g. uncontrolled glaucoma or ocular hypertension, uncontrolled systemic disease such as hypertension, diabetes mellitus, or history of hyperviscosity or hypercoagulability syndromes). Visible retinal pathology as assessed by ophthalmic exam that is considered a risk factor for RVO such as: Evidence of new optic disc cupping Evidence of new visual field defects Intraocular pressure > 21 mmHg 	
		 NOTE: Ophthalmic exam is required for all patients. Exam must be obtained within 28 days prior to registration. 	
	hh.	Patients must not have uncontrolled hypertension (defined as systolic blood pressure > 140 mm Hg and/or diastolic blood pressure > 90 mm Hg which cannot be controlled by anti-hypertensive therapy),	
5.2	Phase	II Portion Eligibility Criteria	
	All the following	same criteria from Section 5.1 above, but eligibility will be restricted to the ng:	
	a.	Patients must have histologically confirmed melanoma with BRAF ^{V600} mutation. Patients must have Stage IIIC or Stage IV disease as outlined in Section 4.0 .	
	. b.	Patients must have received prior BRAF inhibitor therapy (e.g. dabrafenib, vemurafenib) within 56 days prior to registration. Prior trametinib therapy is permitted. Patients are not required to interrupt BRAF or MEK inhibitor therapy prior to the initiation of three agent combination therapy on study.	
	. C.	Patients must have measurable disease as defined in Section 10.1 . All measurable lesions must be assessed (by physical examination, CT, or MRI scan) within 28 days prior to registration. Tests to assess non-measurable disease must be performed within 42 days prior to registration. Patients whose only measurable disease is within a previous radiation therapy port must demonstrate clearly progressive disease (in the opinion of the treating investigator) prior to registration. All disease must be assessed and documented on the Baseline Tumor Assessment Form (RECIST 1.1).	
	d.	Patients must have Zubrod Performance status ≤ 2 (see Section 10.4).	
	e.	No other prior malignancy is allowed except for the following: adequately treated basal cell or squamous cell skin cancer, in situ cervical cancer, adequately treated Stage I or II cancer from which the patient is currently in complete remission, or any other cancer from which the patient has been disease free for five years. Patients with history of RAS mutation-positive tumors are not eligible regardless of interval from the current study. Note : Prospective RAS testing is not required. However, if the results of previous RAS testing are known, they must be used in assessing eligibility.	

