Serum creatinine increase >0.2 mg/dL (18 mcmol/L) BUT ≤0.5 mg/dL (44 mcmol/L) above baseline	 Recheck serum creatinine within 1 week. Serum creatinine increase >1 week: contact CTEP Medical Monitor. If elevation persists beyond 4 weeks, recommend evaluation (consider renal biopsy) for etiology; consider nephrology consultation. If pyrexia is present, treat pyrexia as per guidelines.^a 	Continue study treatment at the same dose level.
Serum creatinine increase >0.5 mg/dL (44 mcmol/L) OR >2 mg/dL (>177 mcmol/L)	 Monitor serum creatinine ≥2-times per week. Hospitalization may be necessary if serum creatinine cannot be monitored frequently. If pyrexia is present, treat pyrexia per guidelines. Consult nephrologist if clinically indicated. Perform renal biopsy if clinically indicated, for example: Renal insufficiency persists despite volume repletion. Patient has new rash or signs of hypersensitivity (such as elevated eosinophil count). 	Interrupt study treatment until serum creatinine recovers to baseline. Restart study treatment.b

^a NSAIDs can induce renal insufficiency, especially in patients with dehydration; ;encourage oral fluids or consider IV fluids as clinically indicated. See guidelines for pyrexia Section 6.1.2.

j. Dose Modification for **Reduced Left Ventricular Ejection Fraction**

Decreases of the left ventricular ejection fraction (LVEF) have been observed in patients receiving trametinib. Therefore, ECHO/MUGA must be performed in regular intervals outlined in the Study Calendar. The same procedure (either ECHO or MUGA, although ECHO is preferred) should be performed at baseline and at follow-up visit(s).

^b Investigator may restart at either the same or a reduced dose level. Escalation of study treatment to previous dose level is allowed if another episode of renal insufficiency does not occur after 4 weeks of dose reduction. Consultation with the Study Chair is required before restarting study treatment if there is evidence of thrombotic microangiopathy.

Treatment Modification and Management Guidelines for LVEF Decrease

Clinic	LVEF-drop (%) or CTCAE grade	Dose Modification

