Pneumonitis has been observed in patients receiving trametinib in combination with dabrafenib. To reduce the risk of pneumonitis, patients will be monitored closely for symptoms, evaluated with imaging and functional tests when appropriate.

	CTCAE Grade
Grade 1	
Grade 2	
Grade 3	
Grade 4	

p. Dose Modification for **Liver Chemistry Changes**

Dabrafenib or Dabrafenib-Trametinib Dose Modification for Liver Chemistry Changes

Dabrateriib of Babrateriib Traffictii	no Dose Modification for Liver Chemistry Changes
Event	Treatment modifications and assessment/monitoring
ALT ≥3x ULN but <5x ULN and TB <2x ULN, without symptoms considered related to liver injury or hypersensitivity and who can be monitored weekly for 4 weeks	 May continue study treatment. Report as SAE if CTEP-AERS reporting criteria is met. If liver chemistry stopping criteria are met any time, proceed as described below.
	MONITORING: Repeat LFT (ALT, AST, ALK, bilirubin) until they return to normal/baseline or stabilise (LFT may be every 2 weeks after 4 weeks if ALT <3x ULN and TB <2 ULN).
 Criteria for discontinuing study drug: When any of the liver stopping criteria below is met, discontinue trametinib and dabrafenib. 1. ALT ≥3xULN and bilirubin ≥2x ULN or >35% direct bilirubin^{1, 2} 2. ALT ≥ 3xULN and INR >1.5, if INR measured² (INR threshold does not apply if subject is on anticoagulant) 3. ALT ≥5x ULN 4. ALT ≥3x ULN persists for ≥4 weeks 	 Immediately discontinue study treatment. Do not restart/rechallenge unless approved by Study Chair. Report as SAE if: 1) CTEP-AERS reporting criteria are met, or 2) patients meet criteria 1-2. Perform liver event ASSESSMENT AND WORKUP (see below). Monitor the subject until liver chemistries resolve, stabilize, or return to baseline (see MONITORING below). If applicable, provide details on required follow up assessments (e.g., follow up for overall survival or disease recurrence or progression). MONITORING: In patients stopping for criteria 1-2 (with abnormal TB

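### An eligible patient with liver metastases and an unchanged ALT of 3 to <5 x ULN meets a mandatory liver stop at about Week 5; a lesser overlap exists for creatinine

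*Combined protocol and SAP*

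**What the plan says.** **Liver, at entry.** Section 5.1n requires "AST and ALT ≤ 2.5 x IULN (or < 5 x IULN for patients with known liver metastases"). For bilirubin it requires "total bilirubin ≤ 1.5 x institutional upper limit of normal (IULN) (or ≤ 2.5 x ULN for patients with Gilbert's syndrome"). Section 5.2 applies the "same criteria from Section 5.1 above, but eligibility will be restricted to the" items listed there, and none of those items alters the liver or renal limits.

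**Liver, on study.** The first row of the Section 8.3p table allows treatment to continue at ALT 3 to <5 x ULN with total bilirubin below 2 x ULN, if the patient has no relevant symptoms and can be monitored weekly for four weeks. That permission lapses once a stopping criterion is met: "When any of the liver stopping criteria below is met, discontinue trametinib and dabrafenib". Criterion 4 is "ALT ≥3x ULN persists for ≥4 weeks". Criterion 1 is "ALT ≥3xULN and bilirubin ≥2x ULN or >35% direct bilirubin". The action column calls for immediate discontinuation and allows rechallenge only with the Study Chair's approval.

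**Renal.** Section 5.1o is met by either a creatinine of at most 1.5 mg/dL or "measured or calculated creatinine clearance ≥ 50 mL/min". Section 8.3i interrupts treatment on "Serum creatinine increase >0.5 mg/dL (44 mcmol/L) OR >2 mg/dL (>177 mcmol/L") and holds it until creatinine has returned to its baseline value.

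**Timing.** Section 9.3 schedules AST and ALT in Phase II at Weeks 1, 5 and 9. The first disease assessment is at Week 9, after two 28-day cycles.

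**The concern.** The 8.3p stopping criteria are absolute multiples of ULN. Baseline appears in that table's monitoring instructions but not in the criteria, and there is no allowance for liver metastases. The entry rule does make such an allowance. The protocol therefore admits a group of patients whose ALT need not change at all for them to meet a mandatory stop.

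Other pairs of limits in the protocol do not collide in this way. QTc must be below 480 msec at entry and action starts at 501 msec. LVEF must be at or above the lower limit of normal at entry, and action needs a value below that limit together with a drop of more than 10% from baseline. This makes the liver overlap look unplanned.

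Two things are at stake. Patients could lose study drug for a pre-existing value rather than for toxicity, about halfway to the first response assessment. Those stops would also be counted in the Section 11.4 summary of patients needing reduction, interruption or discontinuation, which does not separate them from stops for new toxicity.

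**Working it through.** **1. Entry limits against on-study limits**

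| Measure | Entry (5.1n, 5.1o) | On-study trigger (8.3p, 8.3i) | Overlap |
|---|---|---|---|
| ALT, no liver metastases | ≤2.5 x ULN | ≥3 x ULN for ≥4 weeks (criterion 4) | none |
| ALT, liver metastases | <5 x ULN | ≥3 x ULN for ≥4 weeks (criterion 4) | 3 to <5 x ULN |
| ALT, liver metastases | <5 x ULN | ≥5 x ULN (criterion 3) | none |
| Bilirubin, no Gilbert's | ≤1.5 x ULN | ≥2 x ULN, with ALT ≥3 x (criterion 1) | none on this limb |
| Bilirubin, Gilbert's | ≤2.5 x ULN | ≥2 x ULN, with ALT ≥3 x (criterion 1) | 2 to 2.5 x ULN, only if the patient also has liver metastases with ALT ≥3 x |
| Creatinine, clearance route | no ceiling | >2 mg/dL | >2 mg/dL with clearance ≥50 mL/min |

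**2. When the liver stop is reached.** Take an ALT of 3 to <5 x ULN at the Week 1 draw that does not change. Four weeks later is the Week 5 draw, where criterion 4 is met. The Week 9 assessment is four weeks after that. The first row of 8.3p delays the stop but does not remove it, because a stopping criterion overrides it.

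**3. Criterion 1 at entry.** A patient with both liver metastases (ALT 3 to <5 x ULN) and Gilbert's syndrome (bilirubin 2 to 2.5 x ULN) meets criterion 1 as printed, with no waiting period. Footnote 2 to the table puts the >35% direct fraction in parentheses after the bilirubin threshold. That can be read as an added condition rather than an alternative, so this case turns on an ambiguous text.

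**4. Renal band.** The formula in 5.1o is clearance = (140 − age) x weight / (72 x creatinine), times 0.85 for women. Setting clearance to 50 gives the highest eligible creatinine:

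- men: (140 − age) x weight / 3600
- women: 0.85 x (140 − age) x weight / 3600

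This exceeds 2 mg/dL when (140 − age) x weight is above 7200 for men, or above 7200 / 0.85 = 8471 for women.

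- Man, 40 years, 95 kg, creatinine 2.1 mg/dL: 100 x 95 / (72 x 2.1) = 62.8 mL/min.
- Man, 50 years, 90 kg, creatinine 2.1 mg/dL: 90 x 90 / (72 x 2.1) = 53.6 mL/min.

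Both are eligible and already above 2 mg/dL. I read the >2 mg/dL limb as a level, since a rise of more than 2 would be redundant beside a rise of more than 0.5. For these patients the rule is circular: the trigger is met, and so is the condition that ends the interruption.

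**5. Effect on the Phase II decision (illustration only).** Section 11.3 continues after at least 2 responses in 10 and succeeds with at least 8 in 33. Power is the sum over x = 2 to 10 of P(X₁ = x) x P(X₂ ≥ 8 − x), with n₁ = 10 and n₂ = 23. At a true rate of 35% this gives 87.2%, which reproduces the stated 87%.

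The documents give no number of affected patients. As an assumed worst case, let k of 33 have no chance of response, so the rate becomes 0.35 x (33 − k)/33:

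| k | Rate | Power |
|---|---|---|
| 0 | 35.0% | 87.2% |
| 1 | 33.9% | 85.0% |
| 2 | 32.9% | 82.5% |
| 3 | 31.8% | 79.6% |

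**The case against.** The strongest reply is that eligibility governs registration and 8.3p governs what follows, so a site can comply with both in sequence: register the patient, continue under the first row, and stop if ALT has not improved after four weeks. Admitting these patients but stopping those who do not improve could be a deliberate safety choice, and the Study Chair can approve a restart. This stands as far as it goes. It shows that the passages can be operated together. It does not show that the effect was intended, because nothing in the protocol says so.

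A reader might go further than the text allows in four ways.

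- **That the four-week persistence can already be met on Day 1**, because screening values may be 28 days old. Nothing in 8.3p counts time before treatment, and one screening value cannot show persistence.
- **That a patient stopped at Week 5 becomes a non-responder.** Section 9.3 continues scans every 8 weeks off treatment until progression, and best response in Section 10.3 is not restricted to time on treatment. A response can still be recorded.
- **That the renal rule takes patients off study.** It interrupts rather than discontinues. An unchanged patient already satisfies the return-to-baseline condition, and the table's footnote allows a restart at the same dose.
- **That the trial loses a stated amount of power.** The values of k above are arbitrary, and giving those patients no chance of response is a worst case.

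**Conclusion.** The concern holds for the liver limits. The 5.1n allowance and criterion 4 of 8.3p overlap across the whole ALT band from 3 to <5 x ULN in patients with liver metastases, and an unchanged value leads to a mandatory stop at about Week 5 unless a restart is approved. This assumes that ALT stays at or above 3 x ULN on treatment. The case of Gilbert's syndrome with liver metastases is a possible immediate stop that depends on how criterion 1 is read. The creatinine overlap is real but minor: it makes an interruption rule circular and forces no permanent stop.

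The share of patients affected is not given. Reduced exposure before Week 9 follows for anyone stopped. Loss of responses, and of power, is possible but cannot be quantified from the documents. The point merits correction because the text is unclear for identifiable eligible patients, not because the Phase II design is shown to fail.

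**What to change.** Reconcile 5.1n with 8.3p, and 5.1o with 8.3i, so that an unchanged eligible entry value does not by itself trigger discontinuation or interruption. If the present effect is intended, say so explicitly in both places. The sponsor decides which passage moves: the entry limits, or how the on-study limits apply to patients who enter with raised values. In the same amendment, make criterion 1 and footnote 2 of 8.3p agree on the role of the direct bilirubin fraction, and state what ends an interruption under 8.3i when the baseline is itself above 2 mg/dL.

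The cost is a short amendment. If the entry limits are the ones changed, a few patients may become ineligible.
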